Al Triage is available to all GP practices using PATCHS as an optional feature. GP practices must request to have it enabled and undertake specific training on how to use it. Approximately 200 GP practices using PATCHS (20%) currently have Al Triage enabled – the remaining practices use PATCHS without Al Triage. Spectra Analytics are satisfied with the accuracy and clinical safety of PATCHS Al Triage, and plan to offer it to the remainder of practices currently using PATCHS without Al Triage imminently. This presents a unique opportunity to evaluate the impact of Al Triage on delays in urgent and emergency primary care, staff workload, and health inequalities, in a controlled way. This project will also help generate muchneeded high-quality research evidence on Al use in the NHS and aligns with NHS initiatives such as the NHS Al Lab (19). To do this, we (The University of Manchester; UoM) have partnered with Spectra Analytics to conduct a robust study using an interrupted time series analysis and process evaluation.

6) STUDY OBJECTIVES

6.1 Primary Research Question:

1. What is the impact of AI Triage on delays in completing online consultations defined as urgent and emergency by GP practice staff at the patient-level?

6.2 Secondary Research Questions:

Interrupted Time Series Analysis

- 2. What is the impact of AI Triage on the total number of appointments provided by GP practices?
- 3. What is the impact of AI Triage on the number of online consultations submitted by patients?
- 4. What is the impact of AI Triage on the number of online consultations assigned to clinicians?
- 5. What is the impact of Al Triage on emergency department attendances and emergency hospital admissions?
- 6. What are the cost consequences of AI Triage for GP practices and hospitals?

Quantitative Process Evaluation

- 7. What is the fidelity, dose, and reach of AI Triage and online consultations?
- 8. What is the accuracy of AI Triage in intervention practices?
- 9. What is the potential and observed change in triage behaviour?

Both Analyses

10. What is the influence of AI Triage on health inequalities?

7) STUDY DESIGN & PROTOCOL

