patient age, sex, ethnicity, socioeconomic deprivation, and non-English language usage as predictors in our regression model to compare the probability of experiencing a care delay (45). We will also explore the possibility of adding data on patient multimorbidity and frailty if available. If there is a main effect in the outcome analyses, we will also use sub-group models for appropriate interaction terms in the main models to explore the effectiveness of the intervention on population strata of interest described above. We appreciate power will be lower for these investigations so these approaches will be exploratory, and this approach assumes that there is a main effect for the primary and / or secondary outcomes.

Quantitative Process Evaluation

Fidelity, dose, and reach of AI Triage and online consultations

'Fidelity' is whether the intervention is delivered as intended (44). We will evaluate fidelity through counts of how many practices have AI Triage switched on and the number and proportions of staff in each practice that access online learning materials.

'Dose' is how much intervention is delivered (44). We will evaluate dose through descriptive analyses of counts of online consultation usage submissions in both intervention and control practices in terms of overall numbers and specific types of online consultations (for example, health problems or administrative requests). In intervention practices, we will undertake descriptive analyses of counts of predictions made by Al Triage (urgent, emergency, or routine).

'Reach' is the extent a target audience encounters the intervention (44). We will evaluate reach in both intervention and control practices through descriptive analyses of counts of patients that submit online consultations, how many each they submit, counts of staff that process them (including comparisons between clinical and non-clinical staff), and how many each they process. In intervention practices we will include separate counts of staff that process online consultations that have been predicted by Al Triage as urgent or emergency, and how many patients are presented with signpost messages.

[figure not shown]
Al Triage accuracy in intervention GP practices

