 using PATCHS altogether: We will include them in the main analysis in the intervention group. We
 will undertake sensitivity analyses where we use their data as intervention GP practices up to the
 point they cross over and where we exclude them entirely from the analysis.

11.2 Sample Size:

Our sample size calculation is based on our primary outcome measure. Patients and clinicians we consulted during our PPI work felt an absolute reduction of 5% in the proportion of urgent and emergency online consultation delays would be meaningful. Assuming a baseline delay of 25% from our prior research and a simple before-after design, we estimate a minimum of 2928 urgent and emergency (combined) online consultations across both intervention and control GP practices during the intervention period are required to detect a minimum absolute reduction of 5% to 20% with 90% power and 5% alpha. Further assuming 50 urgent and emergency online consultations (combined) on average for a GP practice per month and a 12-month intervention period, this translates to a minimum of three intervention and three control practices. However, this does not account for between-practice variability. Consequently, we will aim to recruit 20 intervention and 20 control practices. Between-practice variability can be difficult to

predict, so we have estimated the power of this sample size for different assumptions of between-practice variance using ipdpower for Stata (48), which calculates power for mixed-effects models using simulations (Table 1). To minimise between-practice variance in our sample, we will recruit intervention and control GP practices in blocks (described in section 8.4). If we find that between-practice variance is high, we will target recruitment of practices with similar baseline characteristics for the outcome measure in subsequent stages.

Table 1: Study power simulations

Between-practice variance	Power (%)	95% confidence interval (%)
0	100	96.4-100.0
0.1	72	62.1-80.5
0.2	53	42.8-63.1
0.825	21	13.5-30.3

12) DATA AND INTERVENTION ACCESS POST-STUDY

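### The models of whether AI Triage's effect on delays differs between patient groups run only after a main effect is found, so the differential-effect part of research question 10 can be lost

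*Protocol*

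**What the plan says.** Section 6.2 of the protocol lists research question 10, "What is the influence of AI Triage on health inequalities", as belonging to both the interrupted time series analysis and the process evaluation. The plain-language summary likewise promises to find out whether the system works alike for patients of different backgrounds.

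Section 11.1 (Interrupted Time Series Analysis, Health inequalities) answers this in two steps:

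- Age, sex, ethnicity, deprivation and non-English language use are entered "as predictors in our regression model to compare the probability of experiencing a care delay". This step is unconditional.
- The step that asks whether the intervention works differently across these groups is conditional: "If there is a main effect in the outcome analyses, we will also use sub-group models". The condition is repeated at the end of the paragraph: "this approach assumes that there is a main effect for the primary and / or secondary outcomes".

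The protocol is open about the status of the second step: "We appreciate power will be lower for these investigations so these approaches will be exploratory".

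**The concern.** Whether an effect varies between groups is a separate question from whether its average is non-zero. An intervention can shorten delays for some patients and lengthen them for others while the average hardly moves. A rule that requires a main effect first drops the analysis in exactly that case, which is the one of most concern for inequality. It also drops it when AI Triage works on average but the main test misses.

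The protocol describes a route by which offsetting could arise. Section 7.2 says that forms predicted as urgent or emergency are sorted to the top of the inbox, so forms that are not flagged move down. If urgent forms from one group were flagged less often, delays could rise for that group and fall for the others. The documents do not show that this happens. It is a reason to look whatever the average result.

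**Working it through.** **1. The plan's own sample size.** Inputs from section 11.2: 25% delayed at baseline, 20% under intervention, 90% power, 5% alpha. Sidedness is not stated, so two-sided is assumed.

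n per group = [1.960 × √(2 × 0.225 × 0.775) + 1.282 × √(0.25 × 0.75 + 0.20 × 0.80)]² / 0.05² = 1464 after rounding up. Two groups give 2928, which is the protocol's figure. The main test is therefore taken below as two-sided at 5%.

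**2. How often the condition is not met, if it means a 5% test on the primary outcome.** Input: "Table 1: Study power simulations", section 11.2, for 20 + 20 practices. It is assumed that the table uses the 5-point effect stated just before it. The printed intervals match exact binomial intervals from 100 simulated studies. Chance not met = 100% − power:

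| Between-practice variance | Power | Not met | Interval (100% minus the table's limits) |
|---|---|---|---|
| 0 | 100% | 0% | 0 to 3.6% |
| 0.1 | 72% | 28% | 19.5 to 37.9% |
| 0.2 | 53% | 47% | 36.9 to 57.2% |
| 0.825 | 21% | 79% | 69.7 to 86.5% |

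**3. Offsetting effects (an assumed illustration, not in the documents).** Take two equal groups of patients, both at 25% without AI Triage. With it, one goes to 20% and the other to 30%.

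- Average with AI Triage: (20% + 30%) / 2 = 25%. The main effect is 0, so a 5% test on this outcome satisfies the condition about 5% of the time.
- Difference between the two effects: 5 − (−5) = 10 points. With 1464 per arm (732 per group), SE = √[(2 × 0.25 × 0.75 + 0.20 × 0.80 + 0.30 × 0.70) / 732] = 0.0319. Power = Φ(0.10 / 0.0319 − 1.96) = about 88%.
- With 20 × 50 × 12 = 12,000 per arm, power exceeds 99%.

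Both powers ignore clustering by practice, so they are upper bounds. They show only that the skipped analysis need not be uninformative.

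With unequal groups the effects cancel only in part. Section 5 reports 21% non-white patients in the early-adopter evaluation. At that split, a 5-point benefit in 79% and a 5-point harm in 21% average to 0.79 × 5 − 0.21 × 5 = 2.9 points. That is smaller than the 5 points assumed for Table 1, and so harder to detect at the same variance.

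**4. If a secondary outcome can also satisfy the condition.** Section 9 lists 16 secondary entries for the interrupted time series (4 binary, 4 time, 6 count, 2 cost). If k outcomes were independent, each tested at 5% with no true effect, at least one would be positive with probability 1 − 0.95^k: 9.8% for 2, 22.6% for 5, 37.0% for 9 and 53.7% for 15. The real outcomes overlap, so this is only a rough range. The figures in step 2 are thus upper bounds under this reading, and the 5% in step 3 would be too low for the condition as a whole.

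**5. What runs without the condition (section 11.1).**

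- Predictors of delay: these relate patient characteristics to delay. No contrast of practice group by period by characteristic is stated.
- Dose and reach by sub-group: these measure use of online consultations, not delay.
- Accuracy by sub-group: this scores predictions against staff decisions.
- Error auditing, including the potential triage decisions in control practices: this concerns misclassification and disagreement.

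None of these estimates AI Triage's controlled effect on delays separately by patient group.

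**The case against.** A reader might infer that research question 10 goes unanswered whenever the main result is null. The documents do not support that. The question spans both analyses, and the four unconditional components in step 5 address much of it.

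A reader might also take 28%, 47% and 79% as the chance that the interaction models are never run. That does not follow either. The text allows a main effect on primary or secondary outcomes to count, it fixes no p-value, and that detail may properly sit in the statistical analysis plan. Table 1 also has a row with no between-practice variance, where nothing is missed. Its variances are alternative assumptions, and the protocol plans recruitment in blocks to keep the variance down.

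Exact cancellation in two equal halves is a constructed case. Finally, five characteristics across many outcomes would produce a large number of weak tests. Some restraint is reasonable, and section 4 (Issue 4) permits out-of-protocol analyses if they are reported as such.

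All of this limits the size of the point, but none of it justifies the condition. A main effect is not a prerequisite for a difference in effect, and requiring one does not control error among the interaction terms. The exploratory label already limits the claims. Multiplicity is better contained by restricting the analysis to one outcome and the five named characteristics. A comparison added after the results are known is also weaker than one fixed beforehand.

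**Conclusion.** The point holds in a limited form. The protocol makes its only stated models of differential effect on delays depend on a main effect, so that part of research question 10 is lost when none is found.

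On the reading of a 5% two-sided test on the primary outcome with a true 5-point effect, the loss occurs in 0% to 79% of studies, depending on between-practice variance. These are upper bounds if a secondary outcome can also satisfy the condition. Under the assumed exact offset, such a test would satisfy it about 5% of the time.

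The conclusion does not depend on these figures. It rests on the stated rule and on the absence of any other model that compares the effect on delays between patient groups. The consequence is moderate, because the analyses are declared exploratory and other inequality work proceeds regardless.

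**What to change.** In section 11.1, Health inequalities, delete the condition for the primary outcome. Fit the interactions of practice group by study period by characteristic for age, sex, ethnicity, deprivation and non-English language use whatever the main result. Report the estimates with confidence intervals and keep them labelled exploratory. Interaction models for secondary outcomes can stay optional, which keeps the number of analyses small.

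The change is one of wording plus five sets of interaction terms. Section 10 already lists the required variables (year of birth, sex, ethnicity, Index of Multiple Deprivation, non-English submission). It also delays transfer of the interrupted time series data until the intervention period has ended, so an amendment made before transfer precedes sight of the results. The downside is a few more imprecise exploratory estimates to report.

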To attempt to reduce these delays in urgent and emergency care, Spectra Analytics developed an Al Triage add-on system for the standard PATCHS product (called 'PATCHS Al Triage' for this document) in project IRAS ID: 264891. PATCHS Al Triage uses natural language processing (NLP) and deep learning to analyse online consultations to predict whether they are either urgent, emergency, or routine based on the above definitions.

PATCHS AI Triage was initially developed in 2020 using 43,998 online consultations for 37,000 patients to 52 GP practices using PATCHS. The unstructured free-text written by patients in their online consultation, type of online consultation submitted (e.g. new health problem, administrative query), and patient demographics were used as inputs to the model. The manually applied 'urgent' and 'emergency' flags from GP practice staff were used as model outputs. Data were split into training (90%) and test (10%) datasets. AI model training was optimised for a high true positive rate based on findings from co-design workshops where GP practice staff and patients felt it was most important that AI Triage systems missed as few urgent or emergency online consultations as possible. The true positive rate of PATCHS AI Triage to detect urgent and emergency online consultations was 86% in the training dataset and 84% in the test dataset. Subsequently in 2021, PATCHS AI Triage was evaluated in 14 early adopter GP practices covering inner city and urban areas in the north and south of England. Using triage decisions made by GP practice

staff to define urgent and emergency online consultations, its true positive rate was 94% in 19,805 online consultations previously unseen by the AI prospectively for 9,725 patients (21% non-white). Qualitative research with 20 staff at early adopter practices showed they found PATCHS AI Triage both acceptable and useful. Work is currently underway to re-train PATCHS AI Triage to ensure its performance has been maintained over time, and scientific publications reporting its development and validation are being prepared for peer-review.

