Control GP practices will continue to use PATCHS without AI Triage as described above and will manually triage patient forms. By default, patient forms are ordered in the inbox by date-time ascending i.e. with the oldest patient forms at the top of the inbox and the newest ones at the bottom. Patient forms are manually triaged by GP practice staff using the categories above, which changes their order in the inbox to aid prioritisation (Appendix 1, Screenshot 2):

- Emergency: adds a red flag icon to the message and sorts it to the top of the PATCHS inbox.
- Urgent: adds an orange flag icon to the message and sorts it to the top of the PATCHS inbox below 'Emergency' forms.
- **Routine**: neither urgent nor emergency. Grey or purple flag icons are added and the position of the message in the PATCHS inbox does not change.

Patients do not receive any additional messages if they submit an urgent or emergency form.

Intervention GP practices: PATCHS with AI Triage (automated triage)

Intervention GP practices will use PATCHS as described above with assistance from the latest version of AI Triage as an add-on feature (called Urgency and Signpost AI in the PATCHS help documentation (27)(28); currently model version 368d85c790a743928be3dd711f914fcc). AI Triage uses the unstructured free-text written by patients in their online consultation, type of online consultation submitted (e.g. new health problem, administrative query), and patient demographics (age and sex) to predict online consultations as either 'emergency', 'urgent', or 'routine'. AI Triage communicates its predictions with GP practice staff and patients in the following ways:

- **GP practice staff**: The manual triage process described above for control GP practices is automated i.e. when patients submit a form that is predicted as emergency or urgent by Al Triage, a red or orange flag icon is automatically added respectively, and the forms are sorted to the top of the PATCHS inbox (Appendix 1, Screenshot 2). The triage decisions (Appendix 1, Screenshot 1) are pre-populated for GP practice staff, which they can change if they disagree (e.g. upgrade or downgrade the urgency).

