We will calculate the overall accuracy (proportion of 'correct' predictions), true positive rate, true negative rate, positive predictive value, and negative predictive value of AI Triage in intervention practices. Our primary measure of accuracy will be for urgent and emergency online consultations combined; secondary measures will assess urgent and emergency online consultations separately. There is no gold standard test to decide the 'correct' triage decision for online consultations written by patients in their own words. We will therefore use the triage decisions made by GP practice staff when processing online consultations and consider their triage decision as 'correct'. Where AI Triage predicts an online consultation as 'urgent' or 'emergency' we will consider it a:

- **True positive** if the triage decision is not changed by staff, or if staff change the triage decision and the highest triage decision applied by staff is 'urgent' or 'emergency'.
- False positive if staff change the triage decision and the highest triage decision applied by staff is
 'routine'.

Where AI Triage predicts an online consultation as 'routine', we will consider it a:

- **True negative** if the triage decision is not changed by staff, or if staff change the triage decision and the highest triage decision applied by staff is 'routine'.
- False negative if staff change the triage decision and the highest triage decision applied by staff is 'urgent' or 'emergency'.

We will quantify cases where emergency online consultations have been predicted as 'routine' as these represent the highest risk misclassifications. The Spectra Analytics Clinical Safety team will investigate these and other patient safety incidents reported by GP practices as per their internal processes to comply with MHRA and NHS DCB0129 standards (16). We will review their findings to understand if there are patient groups or online consultation topics that are at higher risk of misclassification by Al Triage.

Potential triage behaviour change in control GP practices

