We will obtain AI Triage predictions (urgent and emergency – both separate and combined) for control practices for each online consultation submitted during the intervention period and compare them to the actual triage decisions made by GP practice staff using the same definitions of true/false positives/negatives above. These predictions will differ from those in intervention GP practices because they will not have been presented to GP practice staff whilst they processed the online consultations. It identifies a group of patients for whom potentially different triage decisions would have been made if AI Triage had been enabled in those practices. We will then estimate the potential impact of these different triage decisions.

Observed triage behaviour change in intervention and control GP practices

To evaluate observed changes in triage behaviour, we will compare monthly and weekly time series counts of urgent and emergency triage decisions (both separate and combined) made by intervention and control GP practices. In intervention practices we will consider a triage decision as urgent or emergency if the highest triage applied by staff is 'urgent' or 'emergency' or an AI Triage prediction of urgent or emergency is left unchanged (same definition as 'true positives' above). In control practices, we will consider a triage decision as urgent or emergency if the highest triage applied by staff is 'urgent' or 'emergency'. We will also measure counts of patients cancelling their online consultations, and map whether patients cancel their request or receive input from a clinician following a signpost message and/or emergency prediction.

[figure not shown]
Sensitivity analyses

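### In intervention practices every pre-populated AI label that staff leave alone is scored as correct, so the planned accuracy figures are biased upward; in control practices the same rule cannot operate

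*Protocol*

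**What the plan says.** Protocol section 7.2 (Intervention) states that with AI Triage the triage decisions "are pre-populated for GP practice staff, which they can change if they disagree".

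Section 11.1 (AI Triage accuracy in intervention GP practices) concedes that no independent reference exists ("There is no gold standard test to decide the" correct decision) and takes the staff decision as correct. An urgent or emergency prediction is a true positive, and a routine prediction a true negative, on the same condition: it counts as correct "if the triage decision is not changed by staff, or if staff change the triage decision and the highest triage decision applied by staff" falls in the same class. A false positive or false negative arises only when staff change the label to the other class. The section also plans to count emergencies predicted as routine, which it regards as the riskiest misclassification.

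For control practices, section 11.1 (Potential triage behaviour change) will obtain AI predictions that staff never saw and "compare them to the actual triage decisions made by GP practice staff using the same definitions of true/false positives/negatives above". The next analysis in that section (Observed triage behaviour change) uses a different rule for control practices: the highest triage decision applied by staff.

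The process-evaluation sensitivity analyses restrict to clinicians' decisions, use the final decision, or exclude patients who cancelled after a signpost message.

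**The concern.** Because the AI label is the default, deliberate agreement, inattention and never looking at the field are all scored alike, as a correct prediction. A false alarm left in place becomes a true positive and a miss left in place becomes a true negative. If no label were ever touched, every metric would be 100% whatever the AI's real performance.

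Research question 8 (accuracy in intervention practices) rests on this rule. So do the count of emergencies predicted as routine, the subgroup comparisons of accuracy and the error audit: a patient group whose labels staff override less often would appear to be served more accurately. The protocol expects its results to inform wider NHS adoption.

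In control practices the fault is different. No label was displayed, so there was nothing to leave unchanged, and that branch of the borrowed definitions is undefined.

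**Working it through.** The protocol gives no target or expected value for AI accuracy in the study, so there is no planned figure to reproduce. The calculation below illustrates what the scoring rule does.

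**Inputs**
- Prevalence of urgent or emergency forms: 7922/122,504 = 6.47%, stated as 6.5% (section 5).
- Sensitivity against manually applied staff flags: 84%, test set (section 5).
- Specificity: not given; assumed 80%, 90% and 95%.
- Share u of wrong AI labels that staff leave unchanged: not given; assumed 0 to 50%, the same for false alarms and misses.

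**Cells as a share of all forms, specificity 90%**
- TP = 0.065 × 0.84 = 0.0546
- FN = 0.065 − 0.0546 = 0.0104
- FP = 0.935 × 0.10 = 0.0935
- TN = 0.935 × 0.90 = 0.8415

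**Effect of the rule.** Errors left unchanged move to the correct cells: TP′ = TP + u·FP, FP′ = (1 − u)·FP, FN′ = (1 − u)·FN, TN′ = TN + u·FN.

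For u = 0.25: TP′ = 0.0546 + 0.0234 = 0.0780; FN′ = 0.0078; FP′ = 0.0701; TN′ = 0.8441.
- Sensitivity: 0.0780/(0.0780 + 0.0078) = 90.9%, against 84.0%
- PPV: 0.0780/(0.0780 + 0.0701) = 52.7%, against 36.9%
- Specificity: 0.8441/(0.8441 + 0.0701) = 92.3%, against 90.0%
- NPV: 0.8441/(0.8441 + 0.0078) = 99.1%, against 98.8%
- Overall accuracy: 0.0780 + 0.8441 = 92.2%, against 89.6%

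**Range (measured sensitivity / PPV, %)**

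| Assumed specificity | u = 0 | u = 10% | u = 25% | u = 50% |
|---|---|---|---|---|
| 80% | 84.0 / 22.6 | 88.7 / 30.3 | 92.9 / 41.9 | 96.6 / 61.3 |
| 90% | 84.0 / 36.9 | 87.2 / 43.2 | 90.9 / 52.7 | 95.1 / 68.4 |
| 95% | 84.0 / 53.9 | 86.4 / 58.5 | 89.5 / 65.4 | 93.7 / 76.9 |

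**Unequal shares.** Taking u = 25% for one kind of error and zero for the other, at 90% specificity: false alarms only gives sensitivity 0.0780/(0.0780 + 0.0104) = 88.2%; misses only gives 0.0546/(0.0546 + 0.0078) = 87.5%. The direction is the same. The number of misses recorded falls in proportion to the share left unchanged.

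**Sensitivity analyses.** A final decision can still be the untouched default. The protocol does not say whether an untouched default on a form handled by a clinician counts as a decision made by that clinician. Excluding cancelled forms does not bear on the issue. Acceptance of the default is not among the limitations listed.

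**Control practices.** Scored against the staff decision alone, the illustration returns its inputs (sensitivity 84.0%, PPV 36.9% at 90% specificity), with no inflation from this rule.

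**The case against.** The choice of reference is disclosed, and a staff decision is a reasonable one where nothing better exists. Staff are told that they can change a label they disagree with, so an unchanged label may be real agreement; the documents give no rate of passive acceptance. Specificity and u are both assumed. Equal u for both kinds of error has no basis in the protocol, since false alarms are flagged and sorted to the top of the inbox while misses are not. All of this limits what can be said about size. It does not remove the direction, because the rule can only move wrong labels into the correct cells.

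Three stronger readings are tempting, and the documents do not support them.

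- A reader might infer that accuracy is also overstated in control practices and that discordant control cases would be missed. Section 11.1 compares the predictions with actual staff decisions, and its health-inequalities text sets out to find patients whose AI prediction differs from the staff decision. What remains is a definition with a branch that cannot operate.
- A reader might take the rise from the test-set rate ("86% in the training dataset and 84% in the test dataset") to the early-adopter evaluation ("its true positive rate was 94% in 19,805 online consultations") as evidence of the bias. Section 5 does not say whether labels were shown to staff there or how unchanged labels were scored, and the practices and period differ. It is not evidence either way.
- A reader might want the control-practice comparison to replace the accuracy outcome. Research question 8 and section 9 confine accuracy to intervention practices, so replacement would leave that question unanswered.

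**Conclusion.** The point holds for intervention practices. The stated rule puts the index test into its own reference standard and biases accuracy, sensitivity, specificity, PPV and NPV upward, relative to an unprompted staff decision, whenever any wrong label is left in place. It also hides untouched emergencies predicted as routine. The planned sensitivity analyses do not clearly correct this.

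The amount cannot be fixed from the protocol. The illustration rests on an assumed specificity and an assumed unchanged share. PPV is the most sensitive metric: a 25% unchanged share adds roughly 11 to 19 percentage points across the specificities tried (65.4 − 53.9 = 11.5; 41.9 − 22.6 = 19.3).

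For control practices the finding is a wording fault, not demonstrated bias. The whole point concerns a process-evaluation outcome and should be corrected, but it does not touch the primary analysis.

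**What to change.** 1. In intervention practices, report the figures from the section 11.1 rule as agreement with, or acceptance of, the displayed label, and not as accuracy. Restrict them to forms that staff processed. Where the data allow, separate labels that staff actively applied or changed from untouched defaults.
2. Beside them, report the control-practice predictions against unprompted staff decisions, already planned, as the accuracy estimate not contaminated by the displayed label.
3. In the control-practice analysis, replace the cross-reference ("using the same definitions of true/false positives/negatives above") with a rule based only on the highest triage decision applied by staff, as the next analysis in section 11.1 already does, and state how forms with no recorded decision are handled.

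The cost is mainly redrafting, since section 10 already lists AI predictions, staff decisions and processing data for transfer. Whether active confirmation can be told apart from an untouched default depends on what the system records, which the protocol does not state. The downside is that the accuracy figures will look lower, and that unprompted staff decisions are themselves imperfect and come from other practices.
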